Clearing the fog: Is Hydroxychloroquine effective in reducing Corona virus disease 2019 progression: A randomized controlled trial

Registration NO: ID: NCT04491994

Date: 15 May 2020

Study design, setting and participants: This single Centre, parallel open label randomized controlled trial was carried out during 10th April to 31st May 2020 at department of Pulmonology, Pakistan Emirates Military Hospital (PEMH) over 500 patients from both genders between 18-80 years of age. The study design was approved by institutional ethical review committee. The study population was comprised of patients from both genders with Mild confirmed COVID-19 after their written consent. The study protocol and approval documents are available online at ClinicalTrials.gov with trial number of NCT04491994.

Sample size calculation: Sample size was calculated using OPEN EPI with 5% level of Confidence and 80% power to detect a difference and enrolment ration 2:1 between intervention and control group, at a two-sided significance level of $\alpha=0.05$, of 7 days in the median time to clinical improvement between the two groups, assuming that the median time in the SOC group was 14 days and assuming 55% efficacy of HCQ in preventing disease progression and achieving viral clearance at day 7. Calculated sample size was 467, however we used a sample size of 500.

Enrolment procedure: During study period, 672 confirmed PCR positive cases were assessed for eligibility. 132 did not meet selection criteria and subsequently excluded. 540 patients were then enrolled and randomized. Further 20 patients were excluded from analysis as 15 withdrew consent and 5 became symptomatic before first dose of HCQ. During follow up 13 patients were found to be deviated from advised therapy and 7 were lost to follow up yielding a final study population of

500. **Figure 1** summarizes this process. Randomization rules were designed by [name] together with principal investigators and implemented by an independent statistician who was not involved in data analysis. Stratified random sampling was applied to stratify all eligible patients according to age, gender and comorbidities. Computerized random number generator was used and allocation was done in 2:1 sequence. Cards with each group assignment number randomly generated by computer were placed in sequentially numbered envelopes that were opened as the patients were enrolled

Interventions: A total of 349 patients included in intervention group and 151 in control group. In Hospital, HCQ was given to patients after written consent and after considering its contraindications. Three hundred and forty-nine (349) patients were included in intervention group and given HCQ in addition to standard of care treatment. After 12 hours of randomization HCQ was given. Standard dose of HCQ was 400 mg by mouth twice a day for day one followed by 200 mg 12 hourly for next 5 days. The patients who did not give consent for treatment with HCQ or had a known allergy to HCQ or chloroquine or had another known contraindication to treatment with the study drug, including retinopathy, G6PD deficiency and QT prolongation served as controls. Controls were matched with participants on the basis of age, gender and co morbid and comprised of 151 patients. Standard of care (SOC) treatment comprised of daily oral Vit C (2gms), oral Zinc (50mg), oral Vit-D (alfacalcidol 1ug) and tablet Paracetamol (for body aches/fever), intravenous fluids, hemodynamic monitoring, and laboratory testing for SARS-CoV-2 and baseline blood parameters. Neither patients, nor investigators, nor statisticians were masked to treatment assignment. Lab staff who performed sampling for PCR, basic blood tests and other routine measurement were unaware of treatment information. Data regarding age, co-morbidities, history of contact with a positive patient, days since contact, duration of symptoms, PCR status

with date and base line labs/X-ray chest were recorded. Any patient with day 0 CRP greater than 6mg/dl, Absolute lymphocyte count (ALC) < 1000 or evidence of infiltrates on X-ray chest were excluded. Daily temperature, respiratory rate (RR) and resting O2 saturation with pulse oximetry were monitored in all patients during their hospitalization.

Operational definitions: A case was considered confirmed on the basis of positivity of RT-PCR of combined Oropharyngeal and Nasopharyngeal swabs. Severity of disease was defined as per criteria designed by WHO¹¹. Mild disease meant Patients with uncomplicated upper respiratory tract viral infection having non-specific symptoms such as low-grade fever (fever < 100F for < 3 days), fatigue, body aches, cough (with or without sputum production), anorexia, muscle pain, sore throat, nasal congestion, anosmia, headache and rarely diarrhea, nausea, and vomiting. PCR sampling was done on day 7 and 14 of admission. Any chronic health condition for which patients were on prior treatment was considered as co morbidity. After start of treatment, development of fever > 101 F for > 72 hours, shortness of breath by minimal exertion (10-Step walk test), derangement of basic lab parameters (ALC < 1000 or raised CRP) or appearance of infiltrates on CXR during course of treatment was labeled as progression irrespective of PCR status. PCR status of patients was checked after 7 days and 14 days of initiation of treatment.

Inclusion and exclusion criteria: Inclusion criteria included (1) Mild Corona virus disease (COVID-19) (2) PCR confirmed infection (3) Hospital admitted patients (4) 18-80 years age Exclusion criteria were (1) Moderate, severe and critical COVID-19 (2) day 0 CRP greater than 6mg/dl, ALC < 1000 or evidence of infiltrates on X-ray chest (3) comorbidity with life expectancy less than 6 months (4) Contraindications to HCQ therapy.

Outcomes: Primary outcome was disease progression within 5 days of start of treatment. This was defined by development of fever > 101 F for > 72 hours, shortness of breath by minimal exertion

(10- Step walk test), derangement of basic lab parameters (ALC < 1000 or raised CRP) or appearance of infiltrates on CXR. Patients underwent 6 hourly axillary temperature check, daily 10 feet walk test, daily Blood counts, CRP and X-Rays on day 0, 3 and 5.

Secondary outcome was Viral clearance. PCR negativity on day 7 and 14 after admission was recorded.

Statistical analysis: Statistical interpretation of data was performed using Statistical Package for Social Sciences (SPSS) version 23. Results were expressed as mean, standard deviation (\pm SD) for all continuous variables and frequency and percentage for categorical data. We used t-test and chi-square test as appropriate to the nature and distribution of the variables. A p-value < 0.05 was considered statistically significant.

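### The 80% power and the 467 patients are tied to an outcome the trial does not have, and no control progression rate is given, so power for 5-day progression is not established

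*Combined protocol and SAP*

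**What the plan says.** The Sample size calculation paragraph of the combined protocol and SAP gives 80% power, 2:1 allocation and a test "at a two-sided significance level of" 0.05. The difference to be detected is "of 7 days in the median time to clinical improvement between the two groups". The sentence goes on, "assuming that the median time in the SOC group was 14 days and assuming 55% efficacy of HCQ in preventing disease progression"; the control median of 14 days implies 7 days on HCQ. The same 55% also covers viral clearance: "efficacy of HCQ in preventing disease progression and achieving viral clearance at day 7". The paragraph concludes: "Calculated sample size was 467, however we used a sample size of 500".

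Under Outcomes: "Primary outcome was disease progression within 5 days of start of treatment", and "Secondary outcome was Viral clearance", measured as PCR negativity on days 7 and 14. Under Statistical analysis: "We used t-test and chi-square test as appropriate to the nature and distribution of the variables". The Interventions section gives the analysed arms as 349 (HCQ) and 151 (control).

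**The concern.** A power statement needs an outcome, a control value, an effect and a test that belong together. Here they do not. The effect named is on time to clinical improvement, which is not defined or listed as an outcome and has no matching time-to-event analysis. The 55% figure does mention progression, but one number serves both progression and day-7 clearance. It has no 5-day time point, it is not said to be a relative reduction, an absolute difference or a rate in the HCQ arm, and no control rate appears anywhere in the document.

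What is at stake is how the primary result is read. If the comparison of 5-day progression is not significant, a reader will set it against 80% power and cannot know what effect that power refers to.

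**Working it through.** **Inputs from the plan.** Two-sided α = 0.05 (z = 1.960), power 80% (z = 0.8416), allocation 2:1, medians 14 and 7 days, 55% efficacy, calculated N = 467, analysed arms 349 and 151.

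**Step 1. Do the time inputs give 467?** Assume exponential times, so the hazard ratio is 14/7 = 2. Schoenfeld events at 2:1:

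(1.960 + 0.8416)² / [(ln 2)² × (2/3)(1/3)] = 7.849 / (0.4805 × 0.2222) = 73.5, so 74 events.

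The average event probability by day t is [2(1 − 2^(−t/7)) + (1 − 2^(−t/14))]/3. The plan gives no follow-up for this outcome, so t is an assumption:

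| Assumed follow-up (days) | Event probability | N |
|---|---|---|
| 5 | 0.333 | 222 |
| 7 | 0.431 | 172 |
| 14 | 0.667 | 111 |
| 28 | 0.875 | 85 |

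None is near 467, which would need only 74/467 = 16% of patients to have the event. A 1:1 split (66 events), Freedman's formula (71) or a one-sided test (58) lowers the event count further.

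As a t-test on a 7-day difference in means, the control arm would be 467/3 = 155.7, and the SD that gives this is 7 / [2.8016 × √(1.5/155.7)] ≈ 25 days. No SD is stated.

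**Step 2. Does the 55% give 467?** Let p0 be the control rate, p1 the HCQ rate and p̄ = (p0 + 2p1)/3. The Fleiss control-arm size at 2:1 is

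n0 = [1.960 √(1.5 p̄(1 − p̄)) + 0.8416 √(p0(1 − p0) + p1(1 − p1)/2)]² / (p0 − p1)², with N = 3n0.

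Kelsey's formula is n0 = 7.849 × 1.5 p̄(1 − p̄)/(p0 − p1)². Since p0 is missing, solve for the value that returns 467:

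- *55% relative reduction in progression* (p1 = 0.45 p0): p0 = 14.4% (Kelsey), 15.3% (Fleiss) or 16.8% (Fleiss with continuity correction). Check for Fleiss: p0 = 0.153, p1 = 0.0689 and p̄ = 0.0969 give N ≈ 466.
- *55% success in the HCQ arm*: control success of about 41% (0.412, 0.413, 0.408), which is 59% progression. A second solution, about 68–69% control success, would make HCQ the worse arm.
- *55-point absolute difference*: with control progression of 60–95%, N is only 21–35.

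The first two readings match 467 only with a control rate the plan does not give, and those rates are far apart (14–17% against 59%).

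**Step 3. Power for the primary outcome at 349 and 151.** Take 55% as a relative reduction. Exact power sums the two binomial distributions over all tables that the chi-square test rejects. Every control rate below is an assumption:

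| Control progression | Uncorrected chi-square | With continuity correction |
|---|---|---|
| 5% | 39% | 28% |
| 10% | 64% | 56% |
| 15% | 81% | 77% |
| 20% | 91% | 89% |
| 30% | 99% | 98% |

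Power reaches about 80% near 14.5% without correction (0.798) and near 16% with it (0.797).

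**The case against.** The best defence has five parts.

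- *The sentence names prevention of progression, and 467 is attainable for it.* True: under a relative-reduction reading, a control rate near 15% fits. But that rate is obtained by working back from 467; the plan does not state it, and another reading of the 55% fits equally well at a very different rate. The point stands only as a reason not to call 467 wrong.
- *The time inputs were tested with a log-rank model the plan does not use.* Fair. The range of 85–222 rests on exponential times and assumed follow-up, and a t-test with an SD of about 25 days would also return 467. That SD is unstated too, so the time route is not reproducible either, and it still concerns something that is not a trial outcome.
- *A 55-point difference is hard to believe in patients selected for mild disease.* Agreed. It is listed only because the wording does not exclude it, and nothing depends on it.
- *349 and 151 are counts after exclusions, and the plan does not say which chi-square version was used.* Both are correct. The table in Step 3 is therefore power at the analysed size, and it shows both versions.
- *The trial is described as already done, and a non-significant result can be read from a confidence interval.* This limits the harm, since no estimate or test changes. It does not justify leaving an unconditional 80% claim that the document cannot support.

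**Conclusion.** The concern holds. The plan does not establish 80% power for progression within 5 days: the named effect belongs to an outcome the trial does not have, and the only input that mentions progression lacks a control rate, a time point and a scale. As written, the stated inputs do not yield 467 for the primary outcome.

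This is not evidence that the trial is underpowered, nor proof of a slip in the original calculation. If 55% is a relative reduction, uncorrected power at 349 and 151 runs from 39% to 99% as the assumed control rate goes from 5% to 30%, passing 80% at about 15% (about 16% with continuity correction). Because the claim is unconditional and concerns the primary outcome, it must be corrected.

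**What to change.** Replace the paragraph with a two-proportion calculation for 5-day progression at 2:1, two-sided 0.05:

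1. Say whether the 55% is a relative reduction, an absolute difference or a rate in one arm.
2. State the control progression rate originally assumed and its source, or say that none was set. Do not insert a rate worked back from 467.
3. Make the power statement conditional and name the test version. For example: *If 55% is a relative reduction, 349 and 151 patients give at least about 80% power (uncorrected chi-square) when control progression is about 15% or higher, and less below that: about 39% at 5%, 64% at 10%, 81% at 15%, 91% at 20% and 99% at 30%. These control rates are illustrative. With continuity correction the threshold is about 16%.* This describes the analysed sample; it should not be presented as the original design assumption.
4. Delete the median-time input. Give any power for viral clearance separately, with its own control rate.

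The cost is wording and a look-up of the original calculator inputs. No patients are added and the analysis does not change. The price is that an unconditional 80% becomes a conditional, less favourable statement.

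### Forty of 540 randomised patients are removed after randomisation and no all-randomised analysis is described, so the only comparison is in substance per-protocol

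*Combined protocol and SAP*

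**What the plan says.** The Enrolment procedure section reports 672 patients assessed, 132 excluded as ineligible, and 540 enrolled and randomised 2:1 by sequentially numbered envelopes. Two sets of removals follow: "Further 20 patients were excluded from analysis as 15 withdrew consent and 5 became symptomatic before first dose of HCQ", and "During follow up 13 patients were found to be deviated from advised therapy and 7 were lost to follow up". This leaves 500, which the Interventions section gives as 349 on HCQ and 151 controls.

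On timing, the Interventions section says "After 12 hours of randomization HCQ was given". The Operational definitions section counts progression only from treatment start ("After start of treatment, development of fever > 101 F for > 72 hours", among other criteria), and the Outcomes section says "Primary outcome was disease progression within 5 days of start of treatment". No start time is given for controls.

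The Statistical analysis section names the software, the t-test, the chi-square test and a 0.05 threshold. It does not define an analysis set, an intention-to-treat analysis, a missing-data method or a sensitivity analysis.

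The Interventions section also describes the controls in another way: "The patients who did not give consent for treatment with HCQ or had a known allergy to HCQ or chloroquine", or who had another contraindication such as retinopathy, "G6PD deficiency and QT prolongation served as controls". Yet the exclusion criteria include "Contraindications to HCQ therapy".

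**The concern.** Randomisation balances the groups as allocated. Removing patients for something that happened afterwards can undo that balance in either direction, and a chi-square test on those who remain can neither reveal nor correct it. Deviation from therapy and early symptoms may both be related to prognosis, and investigators and statisticians were unmasked.

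The 5 symptomatic patients are the clearest case. Their exclusion is worded around the first HCQ dose, and no matching rule is stated for controls. If the rule worked in the HCQ arm only, it removed early worsening from one side, which would favour HCQ. Their arm is inferred from that wording and is not stated. Becoming symptomatic is not itself a progression criterion, and a fever lasting more than 72 hours cannot be completed within 12 hours. How many of the 5 progressed by day 5 is therefore unknown.

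What is at stake is the primary result. If progression is uncommon, a handful of patients can decide it. If progression is common, they matter little.

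**Working it through.** **Inputs from the documents.** 672 assessed; 132 ineligible; 15 withdrew consent; 5 symptomatic before dosing; 13 deviated; 7 lost; 349 v 151 analysed; 2:1 allocation; two-sided 5% level; 55% efficacy assumed in the sample size section.

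**Not in the documents.** The expected progression rate and the outcomes of the 40. The text gives no removals by arm; Figure 1, not available here, may give them. All rates and arm assignments below are assumptions.

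**Step 1: reproduce the flow.**
- 672 − 132 = 540
- 540 − (15 + 5) − (13 + 7) = 500 = 349 + 151
- All removals: 40/540 = 7.4%
- Without consent withdrawals: 5 + 13 + 7 = 25, and 25/540 = 4.6%
- Removed for reasons that do not in themselves prevent outcome assessment: 5 + 13 = 18, and 18/540 = 3.3%

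**Step 2: no true effect, HCQ-arm events deleted.** Let all 5 belong to the HCQ arm (354 before removal), let k of them progress, and let the true rate be p in both arms. Then apparent RR = [(354p − k)/349]/p.

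| True rate p | k = 5 | k = 2 |
|---|---|---|
| 3% | 0.54 | 0.82 |
| 5% | 0.73 | 0.90 |
| 10% | 0.87 | 0.96 |
| 15% | 0.92 | 0.98 |
| 20% | 0.94 | 0.99 |

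For example, at 5% with k = 5: (17.7 − 5)/349 = 0.0364, and 0.0364/0.05 = 0.73.

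**Step 3: about 55% efficacy, HCQ-arm events restored.** The counts are assumed, and the test is the chi-square without continuity correction. All 5 patients return to the HCQ denominator, with 5 or 2 of them as events.

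| Control rate | Analysed 500 | p | 5 events restored | p | 2 events restored | p |
|---|---|---|---|---|---|---|
| 7% | 11/349 v 11/151 | 0.039 | 16/354 v 11/151 | 0.21 | 13/354 v 11/151 | 0.08 |
| 10% | 16/349 v 15/151 | 0.023 | 21/354 v 15/151 | 0.11 | 18/354 v 15/151 | 0.044 |
| 15% | 24/349 v 23/151 | 0.003 | 29/354 v 23/151 | 0.017 | 26/354 v 23/151 | 0.006 |
| 20% | 31/349 v 30/151 | 0.0006 | 36/354 v 30/151 | 0.003 | 33/354 v 30/151 | 0.001 |

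With all 5 as events, significance is lost at 7% and 10% and kept at 15% and 20%. With 2 as events, it is lost only at 7%. At 10%, at least 3 of the 5 must have progressed (19/354 v 15/151, p = 0.06).

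**Step 4: outer bounds for the 25.** Start from equal rates p in the 500. Upper bound, all 25 as HCQ events: RR = [(349p + 25)/374]/p. Lower bound, all 25 as control events: RR = p/[(151p + 25)/176].

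| p | Upper RR | Lower RR |
|---|---|---|
| 5% | 2.27 | 0.27 |
| 10% | 1.60 | 0.44 |
| 20% | 1.27 | 0.64 |

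**Step 5: does the final split help?** 349/500 = 69.8%, against 66.7% planned (exact binomial p = 0.14). This neither shows nor excludes differential removal. An exact 360:180 allocation would imply 360 − 349 = 11 HCQ and 180 − 151 = 29 control removals, but the documents do not state that allocation.

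**The case against.** The strongest reply is that the 7.4% overstates what can be corrected. Some of the 15 withdrawals may properly stay out, and the 7 lost may have no outcome. Only 13 (13/540 = 2.4%) were dropped for deviating. This stands in part: the set is per-protocol plus complete-case, and 3.3% to 4.6% is the more useful range.

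Second, the examples built on the 5 patients lean one way. Mild disease, the entry condition, is itself defined by symptoms, so becoming symptomatic may not be worsening at all. The endpoint is a broad composite with daily blood tests, so low event rates are not obviously right. One reading of the sample size also points higher: a two-proportion formula with a 55% relative reduction gives about 467 at a control rate near 15%, although other inputs give it too. At 15% the conclusion does not change. All of this stands as a limit on the likely size, but it does not supply the missing analysis.

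Third, under an exact 360:180 allocation no more than 11 HCQ patients were removed, so the upper bounds in Step 4 could not be reached. That is correct under that allocation, which the documents do not state.

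Fourth, starting the window at randomisation changes the stated endpoint. It does, but the present definition gives controls no start time, so a common origin is needed before the arms can be compared.

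Finally, Figure 1 may give removals by arm. Even so, it would not provide an all-randomised analysis.

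**Conclusion.** The concern holds and must be fixed. Forty of 540 randomised patients (7.4%) are removed, some explicitly for events after randomisation, and no all-randomised analysis is described. Confidence in that statement is high.

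Confidence does not extend to the size or direction of the bias. If the 5 symptomatic patients were in the HCQ arm and progressed, their removal favours HCQ, and it could change the conclusion at control rates of about 7% to 10% but not at 15% to 20%. The other removals could push either way.

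The conflict over how controls arose is a separate defect, but it limits what any reanalysis can achieve. If controls were chosen by refusal or contraindication, restoring the 40 would not produce a randomised comparison.

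**What to change.** 1. First reconcile the Interventions account of who served as controls with the envelope randomisation in the Enrolment procedure and with the exclusion of contraindications.
2. Make the primary analysis intention-to-treat by envelope allocation, in all randomised patients who did not withdraw permission to use their data.
3. Count the 5-day outcome window from randomisation in both arms.
4. Keep the 5 symptomatic and the 13 deviating patients in their allocated arms. Classify the 5 over the full window by the same progression criteria as everyone else.
5. For the 7 lost, and for any excluded patient whose outcome was not collected, use multiple imputation and report best-case and worst-case bounds. With so few patients, the bounds will be the more informative part.
6. Give removals by arm and reason in the text if Figure 1 does not.
7. Keep the 500-patient set as a per-protocol sensitivity analysis.

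**Cost.** New analysis-plan wording and a re-run. Day-5 outcomes for up to 25 patients may have to be retrieved from hospital records, and for more if some of the 15 allow use of their data, because the documents do not show that these were collected. The estimate may become less favourable to HCQ, by an amount that depends on the event rate.

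### Mild COVID-19 is defined by having symptoms, yet five randomised patients were removed from analysis for becoming symptomatic; the two statements conflict, and the removal may be one-sided

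*Combined protocol and SAP*

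**What the plan says.** **Who was eligible.** The Inclusion and exclusion criteria section states: "Inclusion criteria included (1) Mild Corona virus disease (COVID-19) (2) PCR confirmed infection". The Operational definitions section explains the term: "Mild disease meant Patients with uncomplicated upper respiratory tract viral infection having non-specific symptoms such as low-grade fever", followed by a list of further symptoms. It has no asymptomatic category. The opening section on design, setting and participants agrees: "The study population was comprised of patients from both genders with Mild confirmed COVID-19 after their written consent".

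**Who was removed.** The Enrolment procedure section gives the flow: "672 confirmed PCR positive cases were assessed for eligibility", "132 did not meet selection criteria and subsequently excluded", "540 patients were then enrolled and randomized". It continues: "Further 20 patients were excluded from analysis as 15 withdrew consent and 5 became symptomatic before first dose of HCQ". A further 13 were removed for deviating from therapy and 7 were lost to follow-up, leaving 500 (349 HCQ, 151 control, per the Interventions section).

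**Related facts.** The Interventions section says that HCQ was given 12 hours after randomisation and that patients and investigators were not masked. Baseline data included "history of contact with a positive patient, days since contact, duration of symptoms, PCR status". Under Outcomes, progression is counted over the 5 days from the start of treatment.

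No section says what *symptomatic* means for the five, lists it as a ground for exclusion or withdrawal, gives their arm, or reports how many patients had symptoms at day 0.

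**The concern.** If mild disease means having symptoms, an eligible patient already has them at entry, so developing symptoms cannot sensibly be a reason for leaving the trial. Two things are at stake.

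- **The comparison between arms.** The five were removed after randomisation because their condition changed, by staff who knew the allocation. The cut-off is the first HCQ dose, an event that does not occur in the control arm. If such patients were dropped only from the HCQ arm, that arm loses early deteriorations that the control arm keeps.
- **The population described.** If people without symptoms were enrolled, the reader needs to know how many stayed in the analysis before applying the result to mild disease.

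**Working it through.** **1. Reproduce the flow.** Inputs are from Enrolment procedure and Interventions.

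- 672 − 132 = 540 randomised
- 540 − (15 + 5) = 520
- 520 − (13 + 7) = 500 analysed
- 349 + 151 = 500

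The counts agree. The five are among the 540 and not among the 500.

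**2. Size of the group.** 5/540 = 0.93% (exact 95% interval 0.30% to 2.15%).

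**3. Set the two statements side by side.**

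| Meaning of *symptomatic* | Status at randomisation | What follows |
|---|---|---|
| First symptoms appeared | No symptoms | The five did not meet criterion 1, and were removed on acquiring what criterion 1 requires |
| Existing symptoms worsened | Eligible | The five were removed after randomisation for a clinical change, under a rule that is not written down |

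Each reading needs a correction, and the text does not say which applies.

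**4. Possible imbalance.** The arm of the five is not stated, so take the extremes. Adding 5 patients to an arm of n analysed patients with observed risk p, all 5 counted as events, shifts the risk by

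(np + 5)/(n + 5) − p = [5/(n + 5)] × (1 − p),

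which cannot exceed 5/(n + 5).

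- All in the HCQ arm: 5/(349 + 5) = 5/354 = 1.4%
- All in the control arm: 5/(151 + 5) = 5/156 = 3.2%

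These are upper limits on the change in one arm's progression risk from this exclusion alone. The arm sizes at randomisation are not given. An exact 2:1 split of 540 would put 360 in the HCQ arm, and 5/360 is also 1.4%. If each of the five had independently a 2/3 chance of being in the HCQ arm, all five would fall there with probability (2/3)^5 = 13%, so chance alone could produce that pattern.

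**5. Can the number of asymptomatic enrollees be derived?** No. On the first-symptoms reading, suppose a share r of asymptomatic enrollees developed symptoms in the roughly 12 hours before dosing. The implied number is 5/r. The values of r are assumptions; the documents give none.

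| r | 5/r | Share of 540 |
|---|---|---|
| 100% | 5 | 0.9% |
| 10% | 50 | 9% |
| 5% | 100 | 19% |
| 1% | 500 | 93% |

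On the worsening reading the number may be zero. The text is compatible with anything from none to nearly all, so it supports no estimate.

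**The case against.** The strongest reply is that this is one loose phrase about 0.9% of the randomised patients, none of whom was analysed. The population is stated to be mild disease, duration of symptoms was recorded, and standard care included paracetamol for aches or fever. All of that points to a symptomatic cohort. Figure 1, which summarises the flow, is not available here and may word the reason differently. A mixed entry population would also limit generalisability without by itself biasing the comparison between arms.

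Much of this stands, and it rules out three stronger readings.

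- **A reader might infer that the analysed cohort was not the defined one, or that the result cannot be assigned to mild disease.** The documents do not support this. No section shows that any of the 500 lacked symptoms, and the recorded symptom duration could settle the question.
- **A reader might infer that at least five asymptomatic people were enrolled.** That holds only on the first-symptoms reading.
- **A reader might want the five counted as progression events.** The outcome as written starts with treatment, and its fever component, which needs more than 72 hours, cannot be completed within a 12-hour gap. Counting them would require a different starting point and evidence that they met a criterion.

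The loose-wording reply still does not dispose of the point. If the word means worsening, the eligibility conflict goes away but an unwritten post-randomisation exclusion remains. Nor does it help to say that the five had moved into moderate disease, an exclusion criterion: the text does not say so, and eligibility had been assessed before the 540 were randomised.

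**Conclusion.** The point holds in a limited form. The symptom-based entry definition and the stated reason for removing the five conflict, and on either reading they were excluded after randomisation for a clinical change, in an open-label trial, on a ground found in no listed criterion. Because their arm is not stated and the cut-off is tied to HCQ dosing, the exclusion may be one-sided. That is a possibility the documents leave open, not something they show.

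The size is small: at most a 1.4-point change in HCQ-arm risk, or 3.2 points in the control arm, assuming all five belonged to one arm and all were events. Baseline symptom status is unreported rather than shown to be wrong. The contradiction is certain from the text; the extent of any asymptomatic enrolment is unknown.

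**What to change.** 1. Reconcile the Operational definitions and criterion 1 with the Enrolment procedure. State what *symptomatic* meant for the five, and give each one's randomised arm.
2. Do not use it as a reason for exclusion. Keep the five in the analysis in their randomised arms, with follow-up for progression counted from randomisation in both arms. If the outcome window stays as it is, add a sensitivity analysis that includes the five. If their outcomes were not recorded, say so and show the result under the extreme assumptions.
3. Keep the reason visible in the participant flow, with its explanation.
4. Report day-0 symptom status by arm, using the recorded duration of symptoms. Contact history cannot serve for this, since it says nothing about symptoms.
5. If asymptomatic patients were enrolled, report progression and PCR clearance by arm within each symptom status, and word the inclusion criterion and conclusion to match.

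**Cost.** Some rewording, one baseline row and a small extra analysis, mostly from data already collected. The group supporting the mild-disease claim may prove smaller than 500.
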